As each patient completes 8 weeks of follow-up, all patient data will be sent to the Mayo Clinic, where an analyst will clean and curate the data made available through the Hugo platform. The analyst will then send the cleaned data for the YNHH patients to the Yale investigator team. The RA will then confirm the primary diagnoses in the YNHH Electronic Medical Record (EMR) for physician visits, emergency department visits, and inpatient admissions during the 8-week period by examining and comparing to the research database to determine if any encounters or diagnoses are missing in the research database.

The data points that we will validate in the Hugo Research Database from the YNHH Epic EMR will be:

- Encounter date
- Encounter type
- Primary diagnosis for encounter

We will also note if any additional physician visits, emergency department visits, and inpatient admissions are seen in either system (in the case of additional points in Hugo, we will also determine if they are from another health system). If any diagnoses are missing in the Hugo Research Database, we will determine from which visit that they were missing.

In addition, we will examine YNHH EMR data to determine what new medications were prescribed at discharge, and then we will examine pharmacy data to determine which of these prescriptions were filled by the patient.

Finally, at the end of the pilot study (i.e. at 8 weeks post-procedure), study participants will be called by the RA and asked to complete a close-out questionnaire (see Appendix) to determine their satisfaction with the process of answering queries and provide the opportunity for them to offer comments and suggestions for

improvement. They will also be asked at what health systems they received care over the past 8 weeks (including hospitalization, emergency department visit, repeat procedure), to assess if all pertinent data was captured in Hugo.

Close-Out Questionnaire, whereby study participants are called by RA at 8 weeks on a HIPAA-protected secure phone line and asked:

- 1. How was your overall experience using this technology (open-ended)?
- 2. How long did it take you, on average, to answer the questions that you were sent weekly?
- 3. How was the experience of answering questions (open-ended)?
- 4. Did you have any of the following in the past 8 weeks:
 - a. emergency department visit
 - b. admission to a hospital
 - c. re-operation
 - d. major complication

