- 5. If yes to #4, what was the reason(s) for the emergency department visit, hospital admission, or re-operation?
- 6. In the past 60 days, at what health systems did you receive medical care? Do you have a portal with access for those health systems?
 - a. For patients who received care in a health system(s) connected to Hugo, we will ask the patient to obtain portal access and then link it to Hugo
 - b. For patients who received care in a health system(s) not connected to Hugo, we will ask the patient to obtain and upload their Continuity of Care Document (CCD) at the end of the study.

At the end of the study period, we will perform additional data abstraction by viewing the YNHH Electronic Medical Record, with the goal of augmenting our understanding of the specific procedures. If notes are available through Hugo at that time, then these notes will preferentially be viewed instead of those in the YNHH Electronic Medical Record. The specific elements that will be abstracted, with the anticipated sources, are as follows:

Pre-Operative History & Physical

-Indications for procedure (for example, for bariatric surgery the patient's BMI and presence of obesity-related co-morbidities; for atrial fibrillation, if the patient has failed pharmacologic therapies)

Operative Notes

- -Bariatric surgeon or cardiac electrophysiologist's technique
- -Additional procedures performed at time of index procedure
- -Medical devices used intra-procedure (if these are not available within the operative note, then we will determine if they can be found in a different place within the YNHH EMR)
- -Device failures or interventions (examples: staple line suturing, clips, or application of fibrin glue; additional devices required)

Discharge Summary

- -In-hospital adverse events
- -Diagnoses (including noting which diagnoses were present on admission and which were co-morbidities)
- -Discharge medications, where the prescribed medications will be compared to the medications that the patient received at discharge

5. Genetic Testing N/A ⊠

A. Describe

- i. the types of future research to be conducted using the materials, specifying if immortalization of cell lines, whole exome or genome sequencing, genome wide association studies, or animal studies are planned *Write here*
- ii. the plan for the collection of material or the conditions under which material will be received *Write here*

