Age, gender, date of birth and several categories of health information (provider encounters, notes, medication lists, problem lists, family history, allergies, laboratory findings, procedures, immunizations, vital signs, and medical record numbers) will be collected via the Hugo application. We will also be collecting data provided and synced to the Hugo application from the wearable devices including the Fitbit Charge 2 (heart rate ambulation and sleep), Nokia Body scale (weight), and the Kardia Mobile EKG (heart rhythm). In addition, we will obtain medication data from 2 major pharmacies.

The research associate will also access the patient's full medical record, with read-only access, within the YNHH Epic electronic medical record (EMR) system. This data will not leave the Epic EMR system in any way, and is only being used to verify certain categories of patient events to confirm that they have been included in the Hugo application. Data access to the YNHH Epic EMR will only be granted after all necessary trainings are complete and sign off is received from the Yale IRB and YNHH medical records department using the Yale New Haven Health System's Research Request for Medical Records Access form.

2.	How will the research data be collected, recorded and stored? After obtaining consent, patients will be requested to submit data from their Hugo personal health records to the study over SSL with a minimum of 128 bit encryption. This data will initially be transferred to Mayo Clinic to a data analyst associated with this project for cleaning. All YNHH patient data will then be shared using Signiant's Media Exchange Managed File Transfer (MFT). This platform is a web-based application used to share data packages over the internet through a secure channel. When being shared, the data will be encrypted using https secure protocol (Appendix). Access to this data will only by available to study personnel at Yale and Mayo Clinic, with collaborators at the Mayo Clinic receiving their own IRB approval.
3.	How will the digital data be stored? □CD □DVD □Flash Drive □Portable Hard Drive □Secured Server □Laptop Computer □Desktop Computer □Other
4.	What methods and procedures will be used to safeguard the confidentiality and security of the identifiable

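### Does the verification-only statement about Epic in Section IV.1 undo the chart abstraction and fill comparison planned in Section I.4?

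*Protocol*

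**What the plan says.** Section IV.1 of the protocol, on protected health information, gives the research associate read-only access to the participant's full Epic record at Yale New Haven Hospital. It then restricts what happens to that information: "This data will not leave the Epic EMR system in any way", and it "is only being used to verify certain categories of patient events to confirm that they have been included in the Hugo application".

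The Research Plan in Section I.4 describes three uses of the same record.

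- **Verification.** A list introduced by "The data points that we will validate in the Hugo Research Database from the YNHH Epic EMR will be" names encounter date, encounter type and primary diagnosis. The check goes a little further: "We will also note if any additional physician visits, emergency department visits, and inpatient admissions are seen in either system".
- **Discharge prescriptions.** "we will examine YNHH EMR data to determine what new medications were prescribed at discharge", after which "we will examine pharmacy data to determine which of these prescriptions were filled by the patient".
- **Abstraction.** At the end of the study, "we will perform additional data abstraction by viewing the YNHH Electronic Medical Record, with the goal of augmenting our understanding of the specific procedures". If Hugo holds the notes by then, "these notes will preferentially be viewed instead of those in the YNHH Electronic Medical Record". If the operative note does not name the devices used, they are looked for elsewhere in the hospital record.

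**The concern.** Section IV.1 states one exclusive purpose, and Section I.4 adds at least one more with a different goal. A surgeon's technique, the indication for a procedure or a device failure is not a check that an event reached Hugo. Someone following Section IV.1 to the letter would not abstract these elements from Epic. Someone following Section I.4 would use the record for a purpose that the confidentiality section rules out.

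At stake would be device, device-failure and in-hospital adverse-event information for patients whose notes never reach Hugo, and possibly the comparison of prescriptions with fills. There is also the question of whether the confidentiality statement describes accurately what is done with the record.

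**Working it through.** The protocol gives no figure to reproduce here, so the check sets the passages side by side and asks what depends on the difference.

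**1. Verification against Section IV.1.** The two agree. The three data points and the note of extra visits are a check of events against Hugo.

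**2. Fill comparison against Section IV.1.** This is ambiguous, not contradictory. Section I.4 lists pharmacy medication data as one of the four sources that Hugo is tested on merging, and both aims in Section I.1 name obtaining pharmacy data. Setting Epic discharge prescriptions against the pharmacy data can reasonably be read as a check of that feed, parallel to the encounter check just before it. Section I.4 says what will be determined (fills) but not why.

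**3. Abstraction against Section IV.1.** Here the conflict is real. The elements are:

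- History and Physical: 1 (indications)
- Operative Notes: 4 (technique, additional procedures, devices used, device failures or interventions)
- Discharge Summary: 3 (in-hospital adverse events, diagnoses, discharge medications)

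The total is 1 + 4 + 3 = 8. Only diagnoses overlaps, in part, with the three-item validation list, so 8 − 1 = 7 fall outside it. That 7 should not be read as a measure of the conflict. Section IV.1 speaks of categories of events and does not tie itself to those three items. Several of the eight also match what Hugo is meant to retrieve anyway, such as coincident procedures, secondary diagnoses, the operative report and the discharge summary. The conflict is one of purpose, and the count adds nothing to it.

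**4. The wording about data staying in Epic.** Taken literally it would also forbid writing down the result of the verification check, which Section I.4 requires. The sensible reading is that chart data are not exported. The statement in Section IV.4 that Yale's data come from the Mayo Clinic likewise reads naturally with Section IV.2, which describes the transfer of Hugo data from Mayo to Yale.

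**5. What depends on the abstraction.** Section I.4 lists 5 enrollment metrics, 5 patient-reported-outcome metrics and 1 device-syncing metric, so 5 + 5 + 1 = 11. None takes a value read from the chart. Of the feasibility items in the two aims, obtaining medical record data is assessed by the verification that both sections allow. Obtaining pharmacy data may draw on the fill comparison. The rest do not use Epic. Section I.13 states no clinical primary outcome.

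**6. Worst case.** If Section IV.1 were applied strictly, the loss would be confined to Yale, where 30 of the 60 patients are planned (30/60 = 50%). Within those, it would cover abstracted elements that Hugo does not supply, plus the fill comparison if that too were ruled out. How many patients this means cannot be derived from the protocol.

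**The case for a change.** The strongest case for a change is that the form asks, in Section IV.1, what health information will be used for the research, and the answer there is exclusive and untrue. Disclosure elsewhere does not make it true. The preference for Hugo notes does not remove the conflict, because Epic remains the source when notes are missing, and the prescription step carries no such preference. The same paragraph makes Epic access conditional on institutional sign-off, so its account of purpose ought to be right. Section I.12 also has device–outcome pairs passed to manufacturers, within 48 hours for one company's devices. Such a pair might surface during abstraction, and forwarding it sits badly with a literal promise that nothing leaves Epic.

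The point about accuracy stands: the exclusive wording does not fit the planned abstraction. The consequence does not follow. The document that restricts the use also sets out the abstraction element by element, so neither study staff nor the review board is left unaware of it. Access to the full record is already granted, so the abstraction needs no wider permission from Section IV.1. The reporting duty rests on the principal investigator becoming aware of an event, and rewording Section IV.1 would not change it. Whether any use exceeds what participants authorized depends on consent and authorization wording that is not at hand, so it can be neither asserted nor dismissed here.

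**Conclusion.** There is one genuine inconsistency: the exclusive purpose in Section IV.1 against the abstraction in Section I.4. It is a clerical slip, most simply explained by a confidentiality sentence written with the verification step alone in mind. The fill comparison is at most ambiguous, and the two remaining wordings are loose, not contradictory.

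No change to the plan follows, because neither way of reconciling the texts brings a gain. Widening the sentence would only describe what Section I.4 already plans. Narrowing Section I.4 would only discard information, possibly including a check that serves the pharmacy aim. Either way, 0 of the 11 listed metrics change, and no sample size, analysis, source of bias or patient-safety outcome improves.

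This rests on two assumptions: that staff follow the detailed Research Plan for what to collect, and that the consent and authorization wording, not shown, is consistent with it.
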